Visit 1: Screening and Baseline Behavioral Assessment. These sessions involve language testing with the OANB (first), picture description, and COWA. This will be the baseline language testing for the first intervention period. Participants with an OANB score that exceeds an average of 80% accuracy will be excluded to leave at least a 20% improvement margin. That is, participants who already score close to ceiling may have limited room for naming improvement. During the first visit, participants will undergo screening assessments. This will determine if they are a candidate for the treatment. If the participant passes the initial screening portion, informed consent will be obtained.

Visit 2: Baseline qEEG and fNIRS. Participants will undergo qEEG brain mapping assessment to obtain baseline EEG analysis to assess brainwave patterns and to identify areas of abnormality compared to normative database of same-age healthy peer group to establish appropriate training goals for neurofeedback sessions. Participants will also undergo fNIRS assessments.

Visit 3-17: Intervention Phase I. These sessions will include the treatment sessions for the first intervention period. Prior to the start of treatment, participants will be randomly assigned to receive either “neurofeedback then sham” or “sham then neurofeedback.” For example, if a participant is randomly assigned to receive “neurofeedback then sham,” the first intervention period of 15 sessions will be neurofeedback training and the second intervention period will be 15 sessions of sham training. Participants will undergo treatment sessions within each intervention phase at a frequency of 2-5 sessions per week as their schedule allows. At each visit within this intervention phase, participants will also receive speech-language therapy (VNeST).

Date: November 11, 2021
Principal Investigator: [name]
Application Number: IRB00242136
NCT# NCT04290988
Study Title: Circuitry Assessment and Reinforcement Training Effects on Recovery (CARTER)

Visits will take approximately 45-minutes for EEG biofeedback training plus an additional 45-minutes for speech-language therapy.

Visit 18: 1-week Post-Intervention Assessment (following Intervention Phase I). This visit will involve post-treatment language testing, qEEG and fNIRS.

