Visit 19-33: Intervention Phase II. These sessions will include the treatment sessions for the second intervention period. The opposite neurofeedback condition will be implemented here. For example, if a participant is randomly assigned to receive “neurofeedback then sham,” the second intervention period will be 15 sessions of sham training. Participants will also receive speech-language therapy (VNeST) during each visit within this intervention phase. Each visit will take approximately 45-minutes for EEG biofeedback training plus an additional 45-minutes for speech-language therapy.

Visit 34: 1-week Post-Intervention Assessment (following Intervention Phase II). This visit will involve 1 week post treatment language testing, qEEG and fNIRS.

Visit 35: Five-Week Post-Intervention Assessment (following Intervention Phase I and II). This visit will include follow-up language testing, qEEG and fNIRS at 5-weeks post-second intervention period.

b. Study duration and number of study visits required of research participants.

Participants will receive treatment for 3-6 weeks (2-5 sessions in a week: total 15 sessions) for each intervention period. There will be one active neurofeedback treatment period and one sham treatment period for each participant with a 1-week washout period in between the two treatment phases. Participants will receive speech-language therapy (VNeST) at each treatment visit (during both active and sham intervention phases). We will assess the participants at baseline and at 1-week follow-up appointments after each treatment period. Participants will undergo a 5-week follow-up appointment following the second treatment period. Study duration will be approximately 15-20 weeks, and the number of visits for each participant will be 35.

c. Blinding, including justification for blinding or not blinding the trial, if applicable.

Randomization and Blinding

The study is to be conducted in a double-blind manner. The participants and the clinician performing the behavioral and physiological assessments will not know the treatment assignment. The PI will have access to the unblinded list of randomization codes and treatment assignments. Technicians performing the active and sham neurofeedback sessions will utilize pre-developed scripts for both active and sham conditions to standardize the prompts utilized within each arm of the study. Participants will answer survey questions throughout each

Date: November 11, 2021

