The primary outcome variable will be the change in number of Content Units (CU) in picture description from baseline to 1-week post-treatment. Hypothesis 1A is: Participants will show greater improvement in CU from baseline to 1-week post treatment, during the EEG neurofeedback condition than during the sham condition.

To test Hypothesis 1A, we will subtract baseline CU from 1-week post-treatment CU, for each condition. We will use a paired t-test to determine if, as a group, patients showed greater increase in CU during the neurofeedback condition compared to the sham condition. We will also carry out paired t-tests for post-stroke aphasia and PPA separately, to determine if the effect was greater in one group.

b. Secondary outcome variables

Hypothesis 1B-F take the form of: Participants will show greater improvement in [outcome variable] from baseline to 1-week post treatment, during the EEG neurofeedback condition than during the sham condition.

To test each hypothesis 1B-F, we will subtract baseline score from follow up scores (1-week post-treatment), for each condition. We will use paired t-tests to determine if, as a group, patients showed greater improvement during the neurofeedback condition compared to the sham condition, at each follow-up. We will correct for multiple comparisons using a Bonferroni correction.

Hypothesis 2A is: We will be able to identify baseline characteristics (demographics and baseline severity measures, as well as qEEG abnormalities) that influence change in the primary outcome measure (change in CU in picture description from baseline to 1-week post-treatment).

To test this hypothesis, we will carry out multivariable linear regression, with the dependent variable (change in CU in picture description from baseline to 1-week post-treatment), and independent variables of age, baseline CU, baseline OANB, baseline COWA, baseline sleep quality, baseline S-anxiety (STAI), brainwave activity (absolute power, peak amplitude frequency) in each frequency band (alpha, beta, theta, delta, gamma) on qEEG.

Hypothesis 2B is: We will be able to identify changes in secondary outcome measures and changes in qEEG that correlate with the primary outcome measure (change in CU from baseline to 1-week post-treatment). These results will allow us to identify variables to explore the mechanisms of the effects.

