To test this hypothesis, we will carry out Pearson correlations between the dependent variable (change in CU in picture description from baseline to 1-week post-treatment), and change in CU, change in OANB, change in COWA, change in absolute power and peak amplitude frequency within each frequency band (alpha, beta, theta, delta, gamma) on qEEG, change in coherence on qEEG (e.g., coherence between left and right hemispheres).

Hypothesis 3A is: Greater improvement in qEEG normalization toward healthy control group (e.g. alpha enhancement with absolute power and peak amplitude frequency ≤ 1.5 standard deviations away from healthy group average) will be observed in the EEG neurofeedback training condition compared to sham training condition.

Date: November 11, 2021
Principal Investigator: [name]
Application Number: IRB00242136
NCT# NCT04290988
Study Title: Circuitry Assessment and Reinforcement Training Effects on Recovery (CARTER)

To test this hypothesis, we will compare baseline and follow-up z-scores for absolute power and peak amplitude frequency of each of the frequency bands (alpha, beta, theta, delta, gamma) by subtracting the absolute value baseline z-score from the absolute value follow-up z-scores for each condition. We will use paired t-tests to determine if, as a group, patients showed greater improvement during the neurofeedback condition compared to the sham condition, at each follow-up. We will correct for multiple comparisons using a Bonferroni correction. We will also carry out paired t-tests for post-stroke aphasia and PPA separately, to determine if the effect was greater in one group.

Hypothesis 3B is: Greater connectivity within the attentional network and the language network (and right hemisphere homologues) will be observed in the EEG neurofeedback training condition compared to sham training condition.

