To test this hypothesis, we will compare baseline and follow-up z-scores for coherence in each of the frequency bands (alpha, beta, theta, delta, gamma) by subtracting the absolute value baseline z-score from the absolute value follow-up z-scores for coherence in each condition. We will use paired t-tests to determine if, as a group, patients showed greater improvement during the neurofeedback condition compared to the sham condition, at each follow-up. We will correct for multiple comparisons using a Bonferroni correction. We will also carry out paired t-tests for post-stroke aphasia and PPA separately, to determine if the effect was greater in one group.

c. Statistical plan including sample size justification and interim data analysis

Statistical Analyses

Statistical tests to evaluate each hypothesis are described above. No interim data analyses are planned, although we will become unmasked to condition after each participant completes the 5 week follow-up

Sample Size Determination

This study is a novel application of neurofeedback for treatment of aphasia, and we have no preliminary data to guide a power analysis. However, we will use this preliminary cross-over study (with each patient as their own control) to identify effect size (if any), in order to plan a randomized, double-blind, parallel, sham-controlled trial. For this preliminary trial, we plan to study 8 patients per year with post-stroke aphasia, and 8 patients per year with PPA, based on our other ongoing trials of post-stroke aphasia and PPA, in which we have found that it is feasible to recruit and retain 8-10 of each per year. We hope to obtain a total of 40 patients with post-stroke aphasia and 40 with PPA over 5 years, to obtain preliminary data for a multicenter, randomized, double-blind, parallel, sham-controlled trial, if the preliminary results are positive.

Missing Data

We plan to minimize missing data by avoiding prolonged intervals between conditions. Most of the study will take place within 7-11 weeks, with each person scheduled to have a 5 week follow up to determine if any changes are long-lasting. To minimize biases, analyses will be by

Date: November 11, 2021
Principal Investigator: [name]
Application Number: IRB00242136
NCT# NCT04290988
Study Title: Circuitry Assessment and Reinforcement Training Effects on Recovery (CARTER)

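### The paired t-tests for 1A-F and 3A-3B carry no period term: precision is lost if gains differ between phases, and the estimate shifts if the sequence split is also uneven

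*Combined protocol and SAP*

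**What the plan says.** Each patient is randomised to an order before treatment starts (Section 4a, Visit 3-17: "Prior to the start of treatment, participants will be randomly assigned to receive either" one order or the other). Phase II repeats the language therapy given in phase I (Section 4a, Visit 19-33: "Participants will also receive speech-language therapy (VNeST) during each visit within this intervention phase").

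The analysis in Section 7 takes a change from baseline in each condition and compares the two conditions within patient:

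- 1A, Section 7a: "We will use a paired t-test to determine if, as a group, patients showed greater increase in CU during the neurofeedback condition".
- 1B-F, Section 7b: "We will use paired t-tests to determine if, as a group, patients showed greater improvement during the neurofeedback condition compared to the sham condition".
- 3A, Section 7b: "follow-up z-scores for each condition. We will use paired t-tests to determine if, as a group, patients showed greater improvement".
- 3B, Section 7b: "z-scores for coherence in each condition. We will use paired t-tests to determine if, as a group, patients showed greater improvement".

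For 1A, 3A and 3B the same test is repeated within each diagnosis. Section 7c adds no further model: "Statistical tests to evaluate each hypothesis are described above". The one regression in the plan (2A) lists neither period nor sequence. No allocation ratio, blocking or stratification by diagnosis is stated. Section 7c, Sample Size Determination, says what the result is for: "to identify effect size (if any), in order to plan a randomized, double-blind, parallel, sham-controlled trial".

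**The concern.** A paired t-test on change scores removes differences between patients, and differences in level between phases. It does not remove a difference in gain between the first and second block. The plan gives reasons why gains might differ: the same therapy runs for 15 sessions and then 15 more, the same tests are repeated, PPA is progressive, and outside speech therapy is recorded by phase but enters no test. None of this shows that a period effect exists.

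If there is one, two things follow. The paired test counts it as error variance. And if more patients complete one order than the other, part of it enters the estimated treatment effect, which is the figure meant to inform the next trial.

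**Working it through.** **The plan's own figure.** 8 patients per diagnosis per year × 5 years = 40 per diagnosis, and 40 + 40 = 80. This reproduces. The plan gives no effect size, SD, alpha or power, so there is no power figure to reproduce.

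**Assumptions, none from the documents.** True effect t = 0.3 SD; two-sided alpha 0.05; no carry-over; L = 0, 0.25, 0.5 or 1; the same L in stroke aphasia and PPA. The SD of the active-minus-sham difference within a sequence is set to 1.

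**Model.** Let D = change under neurofeedback minus change under sham. Its mean is t + L in the neurofeedback-first patients (nAB) and t − L in the sham-first patients (nBA). With p the share in one sequence:

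- shift of the paired estimate = L × (nAB − nBA)/N
- variance of D as the paired test sees it = 1 + 4p(1 − p)L², which is 1 + L² at an even split

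**Even split, 40:40.** The shift is 0. The SD is inflated by √(1 + L²) = 1.03, 1.12 and 1.41 at L = 0.25, 0.5 and 1. That is worth 1 + L² = 1.06, 1.25 and 2 times the patients. Simulated at 100,000 runs per cell:

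| L | Paired power | Adjusted power | Paired type I error |
|---|---|---|---|
| 0 | about 76% | about 76% | 5% |
| 0.25 | about 73% | about 76% | 4% |
| 0.5 | about 68% | about 76% | 3% |
| 1 | about 45% | about 76% | under 1% |

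In one diagnosis group at 20:20, paired power is about 46%, 43%, 36% and 18%, against 46% adjusted.

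**Uneven splits, N = 80.**

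| Split | Shift formula | Shift at L = 0.25, 0.5, 1 | Paired type I error |
|---|---|---|---|
| 44:36 | L × 8/80 | 0.025, 0.05, 0.10 SD | at or below 5% (about 3% at L = 1) |
| 48:32 | L × 16/80 | 0.05, 0.10, 0.20 SD | about 6%, 10%, 16% |

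Adjusted type I error is about 5% in every cell. Under simple 1:1 randomisation a split of 44:36 or worse has a 43% chance, and 48:32 or worse has a 9% chance (exact binomial). In a group of 40, 24:16 or worse has a 27% chance.

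**Averaged over simple 1:1 randomisation.** Paired type I error is about 5% at every L, and the estimate is unbiased.

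**Is a sequence term alone enough?** Only if L is the same in both diagnoses. Take L = +0.5 in stroke aphasia and −0.5 in PPA:

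- At 20:20 in each, power is 68% paired and 68% with a sequence term, so nothing is gained. With diagnosis and diagnosis-by-sequence added it returns to about 75%.
- At 24:16 in stroke aphasia and 16:24 in PPA (40:40 overall), the paired test and the sequence-only model both shift by 0.10 SD and have about 10% type I error. The fuller model has no shift and about 5%.

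**What L measures.** This depends on the phase II baseline. Section 2 has communication tested before and after therapy in each period. The design overview and visit list in Section 4a show one study baseline and then assessments after each phase. If the post-phase-I visit is the phase II baseline, L is a difference between two gains. If the study baseline serves both conditions, it cancels from D, and L becomes minus the whole phase II gain or decline.

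**The case against.** The strongest reply is that the planned test is sound on average. With a realised split near even it is conservative: at 42:38 type I error is about 4%, 3% and 1% at L = 0.25, 0.5 and 1. Inflation needs both a non-zero L and a tail split. The trial is preliminary with no power target, so no promised power is lost. All of that stands, and it is why this is an improvement and not a defect in the error rate.

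A reader might infer that the paired t-tests have an inflated type I error. The documents do not support that: they give no L and no realised split, and over simple randomisation the rate is about 5%. A reader might also infer that sequence allocation is unblocked. The protocol is silent, and Section 4c mentions a list of randomisation codes; silence is not evidence either way. If allocation is blocked within diagnosis, the shift largely disappears among randomised patients and the precision loss remains.

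It is also fair to say that the reasons for a period effect concern language learning and practice. They bear most on 1A-1C and much less on sleep, anxiety, sleep medication, qEEG power or coherence, and the 3A-3B aim is labelled exploratory.

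**Conclusion.** The point holds as a near-free gain in precision and a guard against conditional bias. It does not show that the planned test is invalid or that a period effect exists. The loss is small at L = 0.25 (about 2 to 3 power points at 40:40), material from about L = 0.5 (about 8 points) and large at L = 1 (about 31 points). A shift in the estimate needs a non-zero L and an uneven split together; at 48:32 it is one fifth of L. These sizes rest on the assumed effect, alpha, absence of carry-over and common L. If L differs by diagnosis, a sequence term alone does not deliver the gain. The case is strongest for 1A-1C; for the other outcomes the change does little harm and keeps one method.

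**What to change.** In Sections 7a and 7b:

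1. For each outcome define D = change under neurofeedback minus change under sham, and state which assessment is the baseline for phase II, reconciling Section 2 with Section 4a.
2. Pooled analysis: regress D on sequence (+1/−1), diagnosis (+1/−1) and their product, and test the intercept. This is the equally weighted average effect over the two diagnoses.
3. Within each diagnosis: regress D on sequence and test the intercept.
4. Report the period-adjusted estimate with its confidence interval as the input to the next trial. Keep the paired t-test as a sensitivity analysis.
5. Include sequence and diagnosis in the multiple-imputation model (Section 7c, Missing Data).
6. State the allocation ratio and any blocking or stratification.

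Cost: wording only, no new data, and three degrees of freedom in the pooled model. At L = 0 the noncentrality is 0.3 × √(80 × 4p(1 − p)). Power is 75.5% at 40:40 with 20:20 in each diagnosis, so nothing is lost; it is about 75% at 44:36 and 73.8% at 48:32, a loss of about 2 points. The period term does not remove carry-over across the 1-week wash-out, which is a separate matter.

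### Separate paired t-tests in post-stroke aphasia and PPA cannot show that the effect is greater in one of them, and no direct comparison is planned

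*Combined protocol and SAP*

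**What the plan says.** Section 7a tests Hypothesis 1A in all patients together: "We will use a paired t-test to determine if, as a group, patients showed greater increase in CU" under neurofeedback than under sham. It then adds: "We will also carry out paired t-tests for post-stroke aphasia and PPA separately, to determine if the effect was greater in one group". Section 7b repeats that sentence for Hypothesis 3A (qEEG power and peak frequency) and Hypothesis 3B (coherence). In both places it follows the statement "We will correct for multiple comparisons using a Bonferroni correction", and the text does not say whether the correction extends to the group tests.

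The regression for Hypothesis 2A lists "independent variables of age, baseline CU, baseline OANB, baseline COWA, baseline sleep quality", then state anxiety and the qEEG band measures. Diagnosis is not on the list.

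On numbers, section 7c says "we plan to study 8 patients per year with post-stroke aphasia, and 8 patients per year with PPA" and "We hope to obtain a total of 40 patients with post-stroke aphasia and 40 with PPA over 5 years". It also says "we have no preliminary data to guide a power analysis". No effect size or SD is given, and no significance level or sidedness is stated for these tests.

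**The concern.** Whether an effect is greater in one group is a question about the difference between two effects. A paired t-test within one diagnosis asks whether that diagnosis's effect is zero, and running it twice does not test the difference. One significant and one non-significant result is weak evidence that the effects differ. Two significant results do not show that they are the same.

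The plan therefore poses a question that none of its analyses answers, and it gives no rule for turning the two results into a conclusion. The natural temptation is to report that neurofeedback works in one diagnosis and not in the other. The trial is meant to inform a later multicentre study, so such a claim could affect whom that study enrols, although the documents do not say it would.

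**Working it through.** **1. Sample size.** The plan's figure reproduces: 8 per year × 5 years = 40 per diagnosis, 80 in total.

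**2. Is there a direct comparison elsewhere?** No.
- Section 7c says the tests are those already described, and none of them is a two-sample test or a condition-by-diagnosis interaction.
- The Hypothesis 2A regression omits diagnosis. Its outcome is change in CU from baseline, so adding diagnosis as a main effect would still not test whether the neurofeedback-minus-sham difference varies by diagnosis.
- The secondary objective in section 2 names stroke hemisphere and PPA variant as possible predictors. These divide patients within a diagnosis, and neither appears in the regression list.

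**3. False claims of a difference.** Assumptions, none stated in the plan: the result is read as 'significant in one group only'; tests are two-sided at 5%; both diagnoses have the same true effect d, defined as the mean neurofeedback-minus-sham difference divided by its SD; n = 40 in each.

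The power p of each paired test comes from the noncentral t with 39 df and noncentrality d√40. The groups are independent, so

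P(exactly one significant) = 2p(1 − p),

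which has a maximum of 0.50 at p = 0.50.

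| d (SD) | p | 2p(1 − p) |
|---|---|---|
| 0 | 0.050 | 9.5% |
| 0.2 | 0.235 | 36% |
| 0.3 | 0.457 | 50% |
| 0.4 | 0.694 | 42% |
| 0.5 | 0.869 | 23% |
| 0.6 | 0.959 | 8% |
| 0.8 | 0.9985 | 0.3% |

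Power reaches 50% at d = 0.318. The rate exceeds 20% for d from about 0.12 to 0.51. Simulation (200,000 trials per setting) gave 9.4%, 35.9%, 50.1% and 22.7% at d = 0, 0.2, 0.318 and 0.5. In the same trials a two-sample t-test on the within-patient differences rejected in 4.9–5.0%.

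**4. Sensitivity.**
- With 30 per group the rates are 30%, 46%, 49%, 37% and 20% at d = 0.2 to 0.6.
- With 32, 20 or 8 per group the ceiling stays at 50%, reached at d of about 0.36, 0.46 and 0.80.
- One-sided testing at 5% has the same ceiling, at a smaller d.
- With unequal groups (40 and 20) the rate reaches 54% at d = 0.4.

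**5. Hypotheses 3A and 3B.** If Bonferroni applies, the rate depends on how many tests are counted, which the plan does not state. The smaller families below count one test per measure: 5 bands × 2 measures for 3A, and 5 bands for 3B. The larger ones also count the two group tests per measure. All use n = 40.

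| Family | Level | d = 0.2 | 0.3 | 0.4 | 0.5 | 0.6 |
|---|---|---|---|---|---|---|
| 3A, 10 tests | 0.005 | 10% | 27% | 45% | 49% | 34% |
| 3A, 30 tests | 0.00167 | 5% | 16% | 34% | 49% | 45% |
| 3B, 5 tests | 0.01 | 16% | 35% | 49% | 44% | 25% |
| 3B, 15 tests | 0.0033 | 8% | 22% | 41% | 50% | 38% |

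A stricter level moves the peak to larger effects but does not lower it.

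**6. The opposite error.** Let the true effects be 0.6 and 1.2 SD, with 40 per group at 5%. The powers are 0.959 and essentially 1, so both tests are significant in 96% of trials and this reading detects the real difference in only 4%. The two-sample test, for a difference of 0.6 SD, detects it in 75%.

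**The case against.** The plan never says the groups will be compared by which p-value is significant. Each test also yields a mean difference, and the wording could mean that the two means will be compared by eye, which would suit a study intended to identify an effect size. The 50% arises only near 0.32 SD; the rate is 8% at 0.6 SD and 0.3% at 0.8 SD, and the plan gives no effect size that would place this trial on the curve. None of Hypotheses 1A to 3B posits a difference between the diagnoses, and this is a supplementary analysis in a preliminary trial. The direct test would have low power.

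Much of this is fair. The rates depend on one reading that the plan neither adopts nor excludes, and 50% is a worst case for equal groups. The stakes are limited too. But the main point does not depend on any of these rates. If the intention is to compare the two means, an interval or test for their difference is still needed, and none is planned. Low power for the direct comparison is a reason to show the interval. It does not make two tests of another question an adequate substitute.

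**Conclusion.** The concern holds. The method named in sections 7a and 7b does not serve the purpose stated for it, whatever significance level, effect size or sample size is assumed, and no other analysis fills the gap. If the results are read as significant in one diagnosis only, identical true effects would look different in up to about 50% of trials. That figure assumes equal power in both groups; at a two-sided 5% level with 40 per group it occurs near 0.32 SD. It falls to 9.5% at no effect and below 10% from 0.6 SD upwards. The pooled test of Hypothesis 1A is not affected, so this should be corrected but does not threaten the primary result.

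**What to change.** In section 7a, and under Hypotheses 3A and 3B in section 7b, replace the sentence with wording such as:

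> The within-patient difference (change under neurofeedback minus change under sham) will be compared between post-stroke aphasia and PPA with a two-sample t-test. The estimated between-diagnosis difference with its 95% confidence interval is the main result of this exploratory comparison. Each diagnosis's mean difference with its 95% confidence interval will be reported descriptively.

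For 3A and 3B, add that the Bonferroni correction covers these comparisons, and state the number of tests. State also whether the t-test uses a pooled or an unequal-variance (Welch) estimate. Welch is the safer choice because the plan guarantees neither equal spread nor equal numbers in the two diagnoses.

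The cost is wording only: the plan already calculates the change in each condition for every patient, and diagnosis is known at entry. The limitation is precision. Assuming equal SDs and 40 per group, the 95% confidence interval has a half-width of t(0.975, 78) × √(2/40) = 1.991 × 0.2236 = 0.445 SD. Power reaches 80% only for a difference of about 0.63 SD (0.74 SD with 30 per group; 0.84 SD with 40 per group at a level of 0.005), and is 60% at 0.5 SD and 26% at 0.3 SD. A non-significant result would not show that the effects are equal, which is why the estimate and interval should lead.

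### Holm's step-down could replace Bonferroni for hypotheses 1B-F, 3A and 3B: the same family-wise protection, never fewer rejections, and a gain that runs from nil to about 10 points of power

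*Combined protocol and SAP*

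**What the plan says.** Section 7b (Secondary outcome variables) uses one sentence three times, for 1B-F, for 3A and for 3B: "We will correct for multiple comparisons using a Bonferroni correction". It gives no reason for the single-step form and mentions no stepwise alternative.

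The tests to be adjusted are described as follows.

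- **1B-F** (OANB naming, COWA, PSQI, state anxiety, use of sleep medication): "To test each hypothesis 1B-F, we will subtract baseline score from follow up scores (1-week post-treatment), for each condition". The comparison itself reads: "We will use paired t-tests to determine if, as a group, patients showed greater improvement during the neurofeedback condition".
- **3A**: changes in z-scores for "absolute power and peak amplitude frequency of each of the frequency bands (alpha, beta, theta, delta, gamma".
- **3B**: changes in "z-scores for coherence in each of the frequency bands (alpha, beta, theta, delta, gamma".

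Section 7c adds only that "Statistical tests to evaluate each hypothesis are described above". The documents do not state alpha, sidedness, the number of tests in each family, or whether 1B-F, 3A and 3B are separate families. On sample size, Section 7c says "we have no preliminary data to guide a power analysis" and "We hope to obtain a total of 40 patients with post-stroke aphasia and 40 with PPA over 5 years".

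**The concern.** Single-step Bonferroni holds every test in a family to the strictest threshold, whatever the other results show. Holm's procedure uses the same p-values and starts at the same threshold, but relaxes it after each rejection. It therefore never rejects less, and it controls the family-wise error at the same level.

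Power is worth saving here because the sample was set by recruitment feasibility. The plan also predicts benefit on all five secondary outcomes, and a family in which most effects are real is where Holm gains most. What is at stake is some power for secondary and exploratory results. The primary hypothesis is not involved.

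**Working it through.** **1. The plan's own figure.** The only sizing figure is accrual: 8 per year × 5 years = 40 per diagnosis, and 40 + 40 = 80 in total. This reproduces, but it is not a power calculation, and the plan gives no adjusted threshold to check against.

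**2. Inputs.**
- From the documents: n = 80, each patient in both conditions; paired t-tests; five outcomes in 1B-F; 5 bands × 2 measures = 10 tests in 3A; 5 bands = 5 tests in 3B. These counts are minima. Section 7b also refers to every follow-up, and several sites or electrode pairs would add tests.
- Assumed: two-sided tests, family-wise alpha 0.05, one family per hypothesis group, correlation 0.3 between outcomes, no dropout, real effects of 0.2 to 0.4 SD of the paired difference.

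**3. Thresholds.** Bonferroni uses 0.05/m at every step: 0.05/5 = 0.01 and 0.05/10 = 0.005. Holm orders the p-values and compares the k-th smallest with 0.05/(m − k + 1), stopping at the first failure. For m = 5 the steps are 0.01, 0.0125, 0.0167, 0.025 and 0.05. The first step is the same as Bonferroni's, so Holm helps only after one rejection.

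**4. Error control.** If m0 nulls are true, at most m − m0 rejections can come before the first false one. Its threshold is then at most 0.05/m0, and the family-wise error is at most m0 × 0.05/m0 = 0.05 under any dependence. In simulation with three real effects of 0.4 SD and two nulls, the family-wise error was 2.1% with Bonferroni and 4.2% with Holm. Holm uses more of the allowance but stays within it.

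**5. Anchor for Bonferroni power.** For one test at 0.3 SD the non-centrality is 0.3 × √80 = 2.68. The critical t on 79 degrees of freedom is 2.64 at 0.01 (power about 52%) and 2.89 at 0.005 (about 42%). At 0.4 SD the non-centrality is 3.58 and power at 0.01 is about 82%. The simulated Bonferroni figures below agree.

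**6. Average power per real effect, Bonferroni to Holm** (simulated, n = 80, correlation 0.3):

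| Tests | Real effects | Size (SD) | Bonferroni | Holm | Gain (points) |
|---|---|---|---|---|---|
| 5 | 1 | 0.3 | 52.6% | 52.7% | 0.1 |
| 5 | 2 | 0.3 | 51.8% | 53.5% | 1.7 |
| 5 | 3 | 0.3 | 52.1% | 55.7% | 3.6 |
| 5 | 3 | 0.4 | 82.3% | 85.7% | 3.4 |
| 5 | 5 | 0.3 | 52.4% | 62.7% | 10.3 |
| 5 | 5 | 0.4 | 82.4% | 91.2% | 8.8 |
| 10 | 2 | 0.3 | 42.7% | 43.4% | 0.7 |
| 10 | 10 | 0.3 | 42.7% | 53.2% | 10.5 |

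With all five real at 0.2 SD the gain is about 4 points; at 0.1 SD it is under 1 point. In every setting Holm kept all Bonferroni rejections, and the chance of detecting at least one real effect rose by no more than about 0.1 point.

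**7. Sensitivity to correlation.** With independent tests and all five effects real, the figures are 51.9% to 62.9% at 0.3 SD and 82.2% to 92.2% at 0.4 SD, so the picture does not hinge on the 0.3.

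**The case against.** The strongest reply is that nothing is broken. Bonferroni is valid and pre-specified, and Holm is a preference for a sharper tool. That stands, and it limits this point to an optional improvement.

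A reader might go further and infer that real secondary or qEEG effects will be lost needlessly. The documents do not support that. They give no effect sizes, and the loss is close to nil if only one effect in a family is real. Five listed hypotheses are not evidence of five real effects. Section 3 itself expects behavioural responses to vary between individuals, and the eligibility criteria in Section 5 require a naming deficit but not poor sleep, anxiety or use of sleep medication, so room to improve on 1D-F is not assured. Nor is success on all five outcomes a criterion anywhere in the plan.

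A reader might also take 0.01 and 0.005 as the plan's thresholds. They are inferences: alpha and the families are unstated, and neither method is uniquely defined until they are. Changing the method's name alone would leave that gap open.

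Two further points stand. The consequences are modest, because the trial is preliminary, the aim behind 3A and 3B is labelled exploratory, and 1A is not adjusted. And Bonferroni has simple matching simultaneous intervals, which Holm lacks in an equally simple form. With five tests the Bonferroni interval has level 1 − 0.05/5 = 99%, so a result with p above 0.01 but below its Holm threshold, with every earlier step passed, is Holm-significant beside an interval that includes zero.

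None of this shows any loss of power or of error control from using Holm.

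**Conclusion.** The point holds as a low-cost refinement. Under the assumptions listed, the gain with five tests is about 0 points with one real effect, 2 with two (0.3 SD), 3-4 with three (0.3-0.4 SD) and 4-10 with all five (0.2-0.4 SD). With ten qEEG measures at 0.3 SD it is about 1 point with two real effects and 10 with all ten. Which of these applies cannot be told from the documents. That Holm never rejects less than Bonferroni and holds the same family-wise level depends on none of these assumptions. The primary analysis and all effect estimates, which matter most for planning the next trial, are untouched.

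**What to change.** In the three sentences of Section 7b, replace the Bonferroni correction with a Holm step-down adjustment at family-wise 5%. State that 1B-F, 3A and 3B are three separate families, list the tests in each (outcomes, bands, measures and follow-ups), state the sidedness, and report adjusted p-values.

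Record the change before any outcome is examined by condition. Section 7c says the team is unmasked after each participant's 5-week follow-up, so a later switch could look data-driven.

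The cost is a few lines of text, with no extra patients, visits or data. If simultaneous intervals are kept at the Bonferroni level, say so and note that they can include zero beside a Holm-significant p-value. If the sponsor prefers to keep Bonferroni so that tests and intervals always agree, that is defensible, but the families, alpha and sidedness still need to be written down.
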